In a further related publication [name] et al. found that outpatients with HFpEF had worse QoL and higher anxiety and depression scores compared with HFrEF and non-HF controls. Depression was associated with reduced QoL and was an independent predictor for reduced coordination capacity in these patients ⁴⁹.

Furthermore, we showed recently that novel cardiac markers such as left atrial strain (LAS) might be capable to demonstrate the link between cardiac and peripheral limitations of exercise capacity ⁵⁰. We found in this study in patients with HFpEF and HFrEF that reduced LAS was a sensitive detector for reduced skeletal muscle endurance in these patients with area under the curve AUC (0.8).

Altogether, these data demonstrate that the applicant has ample experience testing exercise function in HF, specifically with cardiopulmonary exercise and skeletal muscle functional testing. Furthermore, the applicant has experience working with muscle tissue and bench science techniques and will be supported by an established group of clinical-translational investigators in the lab of [name].

The next logical step would be to investigate if an intervention such as sauna is safe and if it could reverse these symptoms and manifestations. If this will be proved to be correct, we will plan a larger scale trial.

Our results will likely give a new direction for future research especially in patients with HFpEF This might finally have direct therapeutic implications. We plan as a next step a RCT to confirm our results.

4. AIMS and Hypothesis

The aim of the study is to test the safety and efficacy of intermittent hyperthermia (sauna) in a pilot study on patients with HF. We will compare the results among patients with HFmrEF, and HFpEF regarding cardiac function, exercise capacity, skeletal muscle structure and function, metabolomic changes, cognitive function and quality of life both at baseline and after the intervention with sauna.

Hypothesis: We hypothesize that intermittent hyperthermia (sauna) is a feasible intervention in patients with HF regardless of LVEF. Exploratively we will test the effect of the intervention on filling pressure (E/é) as well as on the level of NT-pro-BNP. Peripherally, skeletal muscle function (including metabolic and mitochondrial function) and structure. Finally, the effects of the intervention on QoL and of cognitive function will be tested.

Questions to be answered through our investigation, and how:

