- 1) Is hyperthermia intervention (sauna) feasible in patients with HF?
- 2) Does sauna improve exercise capacity? (CPET, 6MWT, skeletal muscle strength and endurance).
- 3) Does sauna improve cardiac function (Echocardiography).
- 4) Understanding the related pathophysiology of the observed results on skeletal muscle and exercise capacity on molecular and mitochondrial level (skeletal muscle biopsies and the following tissue analysis parallel to blood analysis).
- 5) The role of inflammation in the altered muscle structure and function and its possible reversibility through sauna. (Skeletal muscle biopsies: NFkB and NEMO).
- 6) Observing changes in QoL and mental health (depression and anxiety). This will be evaluated by questionnaires as well as by testing the hypothesis that correlates Kynurenine to depression and inversely to exercise (here sauna). (Kyn levels both in skeletal muscle biopsy samples and in serum both at baseline and at the end of the intervention).

While the main aim of the current study is to answer the first question, we might get some level of evidence to answer the other questions. This would support planning the next and larger study.

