5. RESEARCH DESIGN & METHODOLOGY

Study Population: HF patients will be recruited from in the clinic of cardiology and angiology in the University Hospital in Magdeburg. The HF outpatient clinic includes a diverse group of both men and women; therefore, study subjects will not be limited by gender. Altogether, 30 patients, 15 in each group will be recruited prospectively and will enter the final analysis. At least 12 patients per group will be analysed with an expected drop-out-rate of 20%. Stratifications will be performed regarding sex and age to guarantee similar distribution in and among these groups.

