Skeletal muscle biopsies: Obtaining muscle tissue from all individuals will allow us to study the effect of sauna on skeletal muscle both structurally and functionally. Skeletal muscle biopsies will be performed by [name], who has performed several series of biopsies (>50 biopsies) without complications. Aspirin, oral anticoagulation as a therapy for atrial fibrillation will be held for two days (the day prior to the muscle biopsy and the day of the muscle biopsy). Other indications for oral anticoagulation are contraindications in our study. Patients will lie comfortably in the supine position for biopsy of the vastus lateralis muscle in the right leg. Biopsy sites will be prepped with betadine and 2% xylocaine (without epinephrine), with a small stab cut then completed with a blade scalpel. A 5 mm Bergstrom muscle biopsy needle will be used to remove 100-200 mg muscle tissue. After harvesting the first sample, the needle will be rotated 90 degrees and a second sample will be extracted to maximize yield for analysis. The wound site will be closed with steri-strips and a sterile pressure bandage. One fragment of the biopsied muscle will be frozen in liquid nitrogen cooled isopentane for histomorphological and enzymatic analysis. The second fragment will be cut and placed in cryotubes containing RNA preservation solution (RNAlater) and immediately frozen in liquid nitrogen. All samples will be stored at -80°C. Analyses will be performed blinded. The patients will be asked to return for reassessment of the wound site ⁵⁹.

A systematic review shows a very low incidence of complications (total 0.15%, 22 complications in the course of 13914 muscle biopsies in children and adults from different muscles [M. quadriceps femoris, M. deltoideus, M. biceps humeri) (Tarnopolsky et al. 2011). These were local skin infections (8 cases), arterial bleeding (2 cases), pain symptoms (>3 days, 5 cases), cutaneous nerve injuries (5 cases), and hematomas (2 cases) ^{60,61}.

All of the following analyses will be performed before and after the intervention.

Oxidative Capacity: Fatty acid oxidation will be analyzed in muscle tissue of all subjects by measuring the production of $[^{14}C]$ CO₂ from $[_{14}C]$ oleic acid.

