9. STATISTICS

There is not enough prior data to calculate the sample size. Our aim is to test primarily the safety of intermittent hyperthermia and the feasibility of the intervention on patients with HF. We still do think based on our previous research and in spite of the small sample volume, that we would find some significant differences in the secondary endpoints comparing baseline data to post intervention.

All data and statistics will be reported as mean \pm standard deviation (n \pm SD) for continuous normally distributed data or as median and interquartile range [25–75%] for variables that were not normally distributed, respectively. Categorical data will be summarized by percentages. The Statistical Package for Social Sciences software (SPSS 26, IBM, Armonk, USA) will be used for statistical analysis. The chi-squared test will be used to look for trend for categorical variables and Kruskal Wallis test will be applied for not normally distributed data, respectively. Analysis of variance (ANOVA), Pearson's or Spearman simple regression will be used as appropriate. A two-tailed p-value <0.05 indicates statistical significance.

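### The protocol expects before-after changes in the same patients, but its rule for non-normal data is Kruskal-Wallis, an independent-sample test, and it names no paired method

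*Protocol*

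**What the plan says.** Two groups, HFmrEF and HFpEF, both receive sauna; there is no untreated arm. Section 4 (Aims and Hypothesis) plans to compare the two groups on cardiac function, exercise capacity, muscle, metabolomics, cognition and quality of life, "both at baseline and after the intervention with sauna". Its list of questions has kynurenine measured in muscle and "in serum both at baseline and at the end of the intervention". For the biopsy work in section 5, "All of the following analyses will be performed before and after the intervention". Table 1 shows the repeat visits, including one at Week 30.

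Section 9 (Statistics) makes no sample size calculation. For the secondary endpoints it expects that "we would find some significant differences in the secondary endpoints comparing baseline data to post intervention". Its next paragraph lists the methods by type of data: chi-squared for categorical variables; for skewed data, "Kruskal Wallis test will be applied for not normally distributed data"; then ANOVA and Pearson or Spearman, where "simple regression will be used as appropriate". Significance is two-sided at 0.05.

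The protocol does not mention a paired t-test, signed-rank test, Friedman test, repeated-measures ANOVA or mixed model.

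**The concern.** Kruskal-Wallis with two samples is the rank-sum test. It treats the baseline values and the post-intervention values as coming from different people. In this design they come from the same people, so the test uses the wrong variance for the difference. The p-value is then miscalibrated whenever the two measurements are correlated, and repeat measurements on a patient usually are, positively.

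The strength of a small before-after study is that each patient serves as his or her own control, and the stated rule discards that. At stake is the significance the protocol expects for its secondary endpoints. Section 4 hopes to draw some evidence from them and says "This would support planning the next and larger study". A change missed because of the test could steer that planning wrongly.

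The point concerns continuous endpoints. The protocol names no binary before-after endpoint, and chi-squared suits percentages compared between groups.

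**Working it through.** **Inputs from the protocol.** Two-sided alpha 0.05 (section 9). Section 5 recruits 15 per group, expects 20% drop-out, and says "At least 12 patients per group will be analysed". These figures agree: 15 × 0.8 = 12. Both groups together give 2 × 12 = 24.

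**Inputs assumed, because the protocol gives none.** Within-patient correlation r of 0 to 0.7; a shift of 0.5 or 0.8 SD; skewed (lognormal) data with log-SD 1, and 0.5 as a milder case. Shift and correlation are on the log scale.

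**Step 1: what the pairing is worth.** With equal SD σ at both visits, the variance of a patient's change is 2σ²(1 − r). An independent-sample test works as if it were 2σ². A shift of d SD is therefore worth d/√(2(1 − r)) SDs of the change score. For d = 0.5:
- r = 0: 0.5/√2 = 0.35
- r = 0.3: 0.5/√1.4 = 0.42
- r = 0.5: 0.5/√1 = 0.50
- r = 0.7: 0.5/√0.6 = 0.65

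The paired test gains as r rises; Kruskal-Wallis does not.

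**Step 2: type I error, by approximation.** For underlying normal data the rank correlation is r_s = (6/π)·arcsin(r/2). Under no change, the rank-sum statistic has variance of about (1 − r_s) instead of 1, so the nominal cut-off of 1.96 acts as 1.96/√(1 − r_s):
- r = 0.3: r_s = 0.288, cut-off 2.32, error about 2.0%
- r = 0.5: r_s = 0.483, cut-off 2.72, error about 0.6%
- r = 0.7: r_s = 0.683, cut-off 3.48, error about 0.05%

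Simulation at n = 24 (20,000 runs) gives 2.2%, 0.7% and 0.1%. The signed-rank test stays at 4.8% to 5.1%.

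**Step 3: power, by simulation** (40,000 runs per cell, log-SD 1, signed-rank on raw differences):

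| Patients, shift | r | Kruskal-Wallis | Signed-rank |
|---|---|---|---|
| 24, 0.5 SD | 0 | 37% | 33% |
| 24, 0.5 SD | 0.3 | 36% | 44% |
| 24, 0.5 SD | 0.5 | 34% | 56% |
| 24, 0.5 SD | 0.7 | 32% | 77% |
| 24, 0.8 SD | 0.3 | 78% | 81% |
| 24, 0.8 SD | 0.5 | 82% | 92% |
| 24, 0.8 SD | 0.7 | 87% | 99% |
| 12, 0.8 SD | 0.3 | 45% | 47% |
| 12, 0.8 SD | 0.5 | 45% | 60% |
| 12, 0.8 SD | 0.7 | 45% | 80% |

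Kruskal-Wallis depends only on ranks, so the degree of skew does not change it. The signed-rank test does better with less skew. At n = 24 and 0.5 SD, log-SD 0.5 gives 47%, 60% and 81% at r = 0.3, 0.5 and 0.7; normal data, or changes taken on the log scale, give 49%, 63% and 84%. On strongly skewed data the two tests break even at about r = 0.1 to 0.25.

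**The case against.** The strongest reply is that section 9 never assigns Kruskal-Wallis to the before-after comparison. The methods paragraph is a generic list sorted by type of data, the same sentence opens with chi-squared, and section 4 plans a between-group comparison for which Kruskal-Wallis is valid. On that reading only an omission remains, and the choice of paired test can be left to a statistical analysis plan.

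That reading is possible, but it is not what the sentence says: the rule covers non-normal data without restriction. If it is meant for groups only, section 9 offers no non-parametric test for the one comparison it expects to be significant. Either way the same short correction is needed. The qualifier in "simple regression will be used as appropriate" belongs to the sentence on ANOVA and regression and does not soften the Kruskal-Wallis rule. Applying Kruskal-Wallis to change scores would test whether change differs between the diagnosis groups, not whether patients changed.

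Several points do stand. ANOVA could be read to include the repeated-measures form, which with two visits is equivalent to a paired t-test. The defect is therefore clearest for endpoints that prove non-normal, and the protocol does not say which those are. The endpoints are exploratory, and the paired data are collected in any case, so the test can still be corrected before analysis. The size rests on assumptions. Section 5 also says that 30 patients enter the final analysis; at n = 30 and 0.8 SD the gap is modest (88% against 90% at r = 0.3, 92% against 97% at r = 0.5), although at 0.5 SD and r = 0.5 it is still 45% against 66%.

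**Conclusion.** The concern holds. The protocol fixes a test that does not fit the comparison announced in the same section, which is more than a detail left open. It should be fixed, but its reach is limited. The error is conservative, concerns continuous secondary endpoints only, and leaves the descriptive statistics and the primary safety and feasibility aim intact.

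The cost is lost power. At a 0.5 SD shift and 24 patients it runs from 8 percentage points (44 − 36) at r = 0.3 to 45 points (77 − 32) at r = 0.7. It shrinks to 3 points (81 − 78) at 0.8 SD and r = 0.3, and there is no loss at r = 0. These figures depend on the assumed shift, correlation and skew. The mismatch between test and design does not.

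**What to change.** In section 9, state that continuous baseline-to-post changes are tested by a paired t-test, or by the Wilcoxon signed-rank test if the changes are not normal, working on the log scale for skewed positive values. For endpoints also measured at Week 30, name a repeated-measures or mixed model, or Friedman's test. Limit Kruskal-Wallis, one-way ANOVA and chi-squared to HFmrEF versus HFpEF comparisons, including comparisons of change scores. Name McNemar's test only if a binary before-after outcome is in fact analysed.

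Before listing the three-visit endpoints, reconcile Table 1 with the text above it. The table shows no isokinetic measurement at Week 30, while the text exempts only the biopsy from the follow-up visit.

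The cost is two or three sentences and one reconciled line. The tests are standard, and the baseline-to-post comparison needs no new data.

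### The single p<0.05 rule in section 9 also covers the omics panels: 188 unchanged metabolites tested one by one would give 9.4 chance 'significant' results per comparison

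*Protocol*

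**What the plan says.** Protocol section 9 gives the only significance criterion in the document: "A two-tailed p-value <0.05 indicates statistical significance". It is not limited by endpoint or platform, and no other section sets a second threshold or mentions a multiplicity adjustment. The same section expects that "we would find some significant differences in the secondary endpoints comparing baseline data to post intervention". For continuous data the difference tests it names are ANOVA and Kruskal-Wallis ("Kruskal Wallis test will be applied for not normally distributed data"). It names no paired test.

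Section 5 (Metabolomic analysis and Lipidomics; Proteomics) plans 188 metabolites in serum, lipidomics in serum and muscle, and an untargeted analysis of the muscle proteome. Metabolite measurements are described for resting serum, post-exercise serum and post-exercise muscle.

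Section 4 announces the comparison: "We will compare the results among patients with HFmrEF, and HFpEF regarding cardiac function, exercise capacity, skeletal muscle structure and function, metabolomic changes", at baseline and after sauna. It also signals that effects are not the main aim: "Exploratively we will test the effect of the intervention on filling pressure", and, beyond feasibility, "we might get some level of evidence to answer the other questions". It adds: "This would support planning the next and larger study".

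**The concern.** A per-test limit of 0.05 suits a handful of named outcomes. Applied analyte by analyte to a large panel, it calls about 5% of the unchanged analytes significant, whatever sauna does. Section 4 frames effects as exploratory. Section 9, where the rule is stated, does not repeat that label and predicts significant findings.

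The primary aim is not at stake. What is at stake is the meaning of the word 'significant' for omics results, and the risk that chance hits influence what the next study measures.

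**Working it through.** The protocol gives no false-positive figure to reproduce, so the check starts from its inputs.

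**Inputs.** Two-sided limit 0.05 (section 9). 188 serum metabolites (section 5, Metabolomic analysis and Lipidomics). 15 patients per group recruited and at least 12 analysed (section 5, Study Population), so 24 to 30 in all. The protocol gives no correlation between metabolites, so a range is assumed.

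**Expected count.** If every metabolite is tested, each test is correctly sized and none truly differs:

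188 x 0.05 = 9.4 false calls per comparison.

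This is a sum of expectations and needs no independence. If all 188 were measured in each of the three sample types or states, the total would be 3 x 9.4 = 28.2.

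**Chance of at least one, independent tests.** 1 - 0.95^188 = 0.99994.

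**Spread under correlation.** 188 unchanged, equally correlated normal metabolites were simulated, 10,000 runs per setting. Settings were paired (n=24, n=30) and between groups (12 vs 12, 15 vs 15). Ranges cover these settings.

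| Assumed correlation | Chance of at least one false call | Median count | 5th to 95th percentile |
|---|---|---|---|
| 0 | at least 0.9999 | 9 | 5 to 14-15 |
| 0.3 | 0.99 | 7 | 2 to 27 |
| 0.5 | 0.89-0.90 | 4 | 0 to 38-41 |
| 0.7 | 0.60-0.62 | 1 | 0 to 49-54 |
| 0.9 | 0.26-0.27 | 0 | 0 to 67-74 |

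The simulated mean was 9.2 to 9.9 throughout, which is 9.4 within simulation error. With strong correlation most panels show few or no chance hits, but about one in twenty shows some 50 or more.

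**Effect of the tests named.** For HFmrEF against HFpEF the expected count stays at 9.4-9.6 (ANOVA) or 9.4-9.9 (Kruskal-Wallis). If these were run as independent-group tests on before/after data, they would be too conservative. The expected count would then be 3.8-4.0, 1.3-1.5 or 0.15-0.21 at within-patient correlation 0.3, 0.5 or 0.7.

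**Effect of a false discovery rate rule.** With Benjamini-Hochberg at 5%, the chance of any false call in a wholly unchanged panel was 0.02 to 0.05 in every setting simulated.

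**What that rule costs.** Assume a paired t-test, independent metabolites, and 10 of 188 truly changed (3,000 runs). The entries are the chance of calling a given changed metabolite significant.

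| True change | n | Unadjusted 0.05 | Benjamini-Hochberg 5% |
|---|---|---|---|
| 0.5 SD | 24 | 0.65 | 0.10 |
| 0.5 SD | 30 | 0.75 | 0.18 |
| 0.8 SD | 24 | 0.96 | 0.65 |
| 0.8 SD | 30 | 0.99 | 0.84 |

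At 0.8 SD and n=24, the unadjusted rule gives about 178 x 0.05 = 8.9 false calls beside 10 x 0.962 = 9.6 true ones, so close to half are false. The simulated average false share was 0.47 at n=24 and 0.46 at n=30. It falls to about 0.05 under Benjamini-Hochberg.

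**The case against.** The strongest reply is that this is an exploratory pilot, that false discovery control for omics data is ordinary content of a statistical analysis plan, and that such a plan may exist unseen. On this view the 0.05 sentence is a generic per-test convention. The reply is right that unadjusted p-values are defensible in exploratory work and that a missing procedure alone would be no finding. But the protocol does not leave the criterion open. It defines statistical significance without restriction, and a later plan that reserved the word for adjusted results would depart from that definition.

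Second, nowhere does the protocol say the metabolites will be tested one at a time. The earlier work illustrated in section 5 used heat maps and PLS-DA, and the secondary endpoints are never listed. That stands, so the 9.4 is conditional. Section 9, however, names only conventional tests and no multivariate method.

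Third, for the before/after comparison that section 9 stresses, independent-group tests would give fewer chance hits than 9.4. That also stands, but it would come from an ill-fitting test, and the comparison between the two heart failure groups is unaffected.

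Finally, adjustment is costly for modest effects, and the protocol mentions more analytes than the three proposed below for separate reporting. Both are fair points and bear on how the change is worded.

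**Conclusion.** The concern holds and is minor. As written, section 9 attaches statistical significance to about 5% of unchanged analytes on every panel tested analyte by analyte: 9.4 on average per comparison for the 188 metabolites. This assumes separate, correctly sized tests and no true differences. The mean does not depend on correlation, but the spread and the chance of any false call do, and those figures rest on assumed correlations. Lipidomics and proteomics fall under the same rule, but their analyte numbers are not given and no count is offered for them. The safety and feasibility conclusions do not change.

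**What to change.** Amend section 9 as follows.

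1. For metabolomics, lipidomics and proteomics, control the false discovery rate by Benjamini-Hochberg within each platform and comparison, for example at 5%. Call only results that pass it significant. Show unadjusted p-values beside them so that signals for later study are not lost.
2. Report separately, as pre-specified, the analytes the protocol already singles out: kynurenine (section 4 plans "Kyn levels both in skeletal muscle biopsy samples and in serum both at baseline and at the end of the intervention") and atrogin-1 and MuRF-1 (section 5, mRNA Expression, as the particular focus). If the sponsor wants others on this list, they should be named before the data are analysed.
3. Repeat in section 9 the exploratory status given in section 4. This part is editorial.

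The cost is one or two sentences and one routine analysis step, with no new data and no change in conduct. The drawback is the loss of sensitivity shown above, which is severe for changes near 0.5 SD and is the reason to keep unadjusted p-values visible.

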10. ETHICAL ASPECTS OF PROPOSAL

Participation is entirely voluntary and will in no way effect their care. There is no direct benefit to the patients except a strong contribution to science.

All efforts will be made to minimize risk to the subject. The cardiopulmonary test and Biodex muscle function testing will occur in the outpatient clinical area. Emergency equipment and medical personnel will be in the immediate vicinity. Risks associated with skeletal muscle sample collection are very small. Blood samples will be taken during the outpatient visits at low risk. Adverse events will be reviewed on a biweekly basis by a cardiologist otherwise not affiliated with this proposal. Serious adverse events will be reported to the Institutional Review Board within 24 hours. All patient information is kept absolutely confidential.

